VERSION DATE: 22 FEB 2023

ABBREVIATIONS/DEFINITIONS

- AE: Adverse Event
- CES-D: Centers for Epidemiological Studies 20-item scale
- DAST: Drug Abuse Screening Test
- FTND: Fagerstrom Test for Nicotine Dependence
- HPHC: Harmful and Potentially Harmful Constituents
- IUD: Intrauterine Device
- IVRS/IVR: Interactive Voice Response System
- MAST: Michigan Alcohol Screening Test (Short form)
- SAE: Serious Adverse Event
- UB: Usual Brand

1.0 Objectives

To investigate a comprehensive set of abuse liability and appeal measures, smoking intensity, as well as analyze the impact of sugar content on the formation of DNA adducts derived from aldehydes and oxidative stress in the oral cavity of smokers.

2.0 Background

Chemical constituents of tobacco and cigarette smoke play crucial role in addictiveness, toxicity and carcinogenicity of tobacco products. The U.S. FDA established a list of 93 harmful and potentially harmful constituents (PHPC) in tobacco and cigarette smoke that cause or have potential to cause these and other harmful effects.¹ Levels of many PHPCs in cigarette smoke can be substantially reduced by modifying cigarette manufacturing approaches.² However, in the absence of regulation, smokers are being exposed to variable and often unnecessarily high levels of such constituents. According to the Family Smoking Prevention and Tobacco Control Act, the FDA can set standards for PHPCs.³ Such regulation is likely to serve as a powerful tool in efforts to protect public health. As an example, reduction of nicotine in cigarette tobacco can reduce abuse liability of cigarettes.⁴ In addition, prospective epidemiological studies have shown that the level of intake of some tobacco carcinogens is predictive of the risk of cancer development in smokers, suggesting that limiting smokers' exposures to such constituents may be beneficial.⁵⁻⁷ Therefore, imposing standards for constituents that contribute to addictive and toxic properties of cigarette smoke can potentially help to reduce smoking prevalence and/or minimize harmful exposures in smokers who are unable or unwilling to quit.

Soluble sugars such as sucrose, fructose, glucose are formed via enzymatic hydrolysis of starch in tobacco material during its processing, and are also added to tobacco blend during cigarette manufacturing.⁸ Tobacco manufacturers also use a variety of other sugar-containing ingredients such as brown sugar, honey, corn syrup, and molasses.^{8, 9} During cigarette combustion, processes such as Maillard reactions and sugar caramelization and pyrolysis can result in the formation of a variety of products (Figure 1), including aldehydes (e.g., formaldehyde, acetaldehyde, acrolein), furans (e.g., 2,5-dimethylfuran, furfural and 5-hydroxymethylfurfural), other volatile compounds (e.g., benzene, acrylamide, polycyclic aromatic hydrocarbons), ketones (e.g. diacetyl), and acids (e.g., formic and acetic acid). Therefore, sugars in tobacco filler are likely to have a profound impact on cigarette smoke properties. First, the majority of the products of sugar decomposition are important *toxicants and carcinogens*.^{10-18,21} In addition, some volatile products of caramelization and acids formed during sugar pyrolysis play an important role in *palatability-related smoke*.

MEDICAL PROTOCOL (HRP-590)

PROTOCOL TITLE: Sugars Project

VERSION DATE: 22 FEB 2023

[figure not shown]

Figure 1. Some of the products of sugar pyrolysis discussed in this proposal.

characteristics such as flavor, taste, and harshness. Flavor and taste can be influenced by diacetyl and other products of Maillard reaction (and subsequent Amadori rearrangement) and caramelization.⁸ Acetic acid and formic acid, the most abundant pyrolytic products of sugars, can contribute to palatability of smoke by lowering its pH and reducing its harshness. This is particularly important for American blended cigarettes which contain Burley tobacco that yields harsh smoke with high pH.^{22, 23} Indeed, tobacco manufacturers are using various sugars as casings with the purpose of balancing and enhancing these sensory qualities and developing specific taste and flavor characteristics for cigarette brands.²²⁻²⁴ Lastly, acetaldehyde and potentially other products of sugar decomposition may contribute to *addictiveness* of cigarette smoke. For example, acetaldehyde increases dopaminergic neuronal activity and enhance nicotine self-administration in laboratory animal studies.^{25, 26}

For a tobacco constituent to be considered for potential regulation, it is important that there are known approaches to its control and/or reduction in tobacco products. American blended cigarettes typically contain a mixture of tobaccos cured by different methods; therefore, levels of "natural" sugars in tobacco filler can be reduced by adjusting tobacco blending and processing practices. For example, it is known that curing tobacco at elevated temperatures prevents sugar metabolism and results in higher sugar content in tobacco: 8-30% of tobacco weight in flue-cured Virginia tobacco and 10-20% in sun-cured Oriental tobacco. In contrast, processed Burley tobacco is low in sugars (<0.2%) because it is subjected to air-curing, a slow processing method which allows sugars to be metabolized through enzymatic processes.^{22, 27} Compensation for such losses is one of the main reasons why manufacturers add sugars in cigarette manufacturing. Ban on added sugars is another, obvious approach to sugar content reduction in tobacco filler.

MEDICAL PROTOCOL (HRP-590)

PROTOCOL TITLE: Sugars Project

VERSION DATE: 22 FEB 2023

To summarize, as precursors to smoke constituents that play important roles in smoke toxicity, carcinogenicity, palatability, and addictiveness, *sugars are likely the most versatile key constituents contributing to the smoking-associated morbidity and mortality*. Manufacturer reporting of sugar levels in tobacco products could be required by the FDA if sugars are added to HPHC list, which would allow for a more accurate characterization of harmful potential of cigarettes and other combustible or heated tobacco products. Furthermore, reductions of sugar content in cigarette tobacco could potentially result in decreased palatability of cigarette smoke, make it harder to inhale due to increased harshness, and reduce levels of certain volatile toxicants and carcinogens.

3.0 Study Endpoints/Events/Outcomes

3.1 Primary Endpoint/Event/Outcome

To evaluate the impact of sugar content on smoking intensity (nicotine levels in spent filters), subjective responses to cigarettes (e.g., reinforcing and sensory effects) and behavioral measures (multiple choice procedure, cigarette purchase task). We hypothesize that the collected measures will indicate lower abuse liability for cigarettes with lowest sugar content.

3.2 Secondary Endpoint(s)/Event(s)/Outcome(s)

To conduct an exploratory analysis of the relationship between sugar content in study cigarettes and levels of aldehyde- DNA adducts in oral cells of study participants after smoking these cigarettes. Aldehydes are known to cause respiratory tumors in laboratory animals and DNA adducts in the human lung^{10,11,14}

4.0 Study Intervention(s)/Investigational Agent(s)

4.1 Description of study cigarettes

Winston brand cigarettes will be modified by adding a mixture of sucrose to each cigarette at 2 levels so that the amount of total (originally present and added) sugar content in these cigarettes matches median and highest levels found in popular brands analyzed in Aim 2. For example, median and highest levels of the sum of sucrose, glucose, and fructose in the CDC publication were 5.7% and 8.9% (w/w), respectively, across the 20 unidentified brands.⁵⁰ The brand #19 in that study has the lowest sum of these sugars at 3.3% w/w. This allows for addition of sucrose to this brand at 2.4% and 5.6% w/w to achieve median and highest levels in that study. We will use similar calculations to determine the amount of sugars to be added to study cigarettes in this laboratory study.

Medicinal-grade ultrapure sucrose manufactured under GMP standards will be used for the modification of Winston cigarettes. The prepared cigarettes will be conditioned at 25 °C and 60% relative humidity for 2 days, and then stored at 4 °C until their use in study procedures. We used this approach in our previous studies in which we added NNK to cigarettes that were smoked by study participants under the FDA Center for Tobacco Products Protocol Number P00006.

MEDICAL PROTOCOL (HRP-590)

PROTOCOL TITLE: Sugars Project

VERSION DATE: 22 FEB 2023

4.2 Handling of Study Cigarettes

The finished study cigarette product will be packaged by the [name] laboratory in sterilized tins containing 3 (1 extra) cigarettes with a label that encodes the level of sugar content, which will remain blind to the study investigators. The tins will be transported to the research clinic. The number of cigarettes transported from the laboratory to the clinic will be recorded at the lab and then at the clinic upon receipt. At the clinic, the cigarettes will be refrigerated until their use at 4 degrees Celsius. Any temperature variations over +/- 3 degrees C will be discussed with PI to determine if the product freshness has been impacted. Upon participant randomization, the appropriate tin with a specified label will be pulled from the refrigerator. The label on the tin will be put in the participant's case report book and recorded on the product distribution log. All unused cigarettes will be destroyed and disposed of.

4.3 **Biosafety:** NA

4.4 **Stem Cells:** NA

4.5 **Fetal Tissue:** NA

5.0 Procedures Involved

5.1 Study Design

Overview: Participants (N=30 completers) will complete a baseline visit where they will smoke their usual brand cigarette. In the next three sessions, they will receive one of three study cigarettes with varying sugar content (low, medium and high) in a double-blind manner and counterbalanced order across participants. In each session, participants will first smoke either their usual brand cigarettes (at baseline) or their assigned study cigarette (subsequent sessions) in a regimented manner: 10 puffs total, 30 seconds between puffs. There will be a one-hour interval since the time of cigarette extinction before smoking the next cigarette. After this interval, participants will smoke their assigned cigarette *ad libitum* within a 10 minute time period. Safety and subjective measures will take place during this session as described below.

Anticipating a 60-65% attrition rate based on current experiences, we will recruit up to 75 participants.

Study Procedures: Smokers who smoke at least 5 cigarettes/day will attend 4 laboratory sessions during which they will be asked to smoke their usual brand (UB) cigarettes and then one of three study cigarettes with low, medium and high levels of sugar in separate sessions using a within-subject design with conditions counterbalanced determined by a Latin square. In each session, smokers will be asked to smoke a cigarette in a standardized manner (10 puffs, 30 second interval between puffs) and 1 hour later, *ad libitum*. Each of the sessions will be separated by at least 48 hours but not more than 5 days. The proposed study design has been used to assess the abuse liability of electronic cigarettes compared to other tobacco/nicotine products,⁹⁹⁻¹⁰¹ that vary in flavors and modified risk claims,¹⁰² and that vary in menthol

MEDICAL PROTOCOL (HRP-590)

[figure not shown]
PROTOCOL TITLE: Sugars Project

VERSION DATE: 22 FEB 2023

concentration and nicotine dose.¹⁰³ This design is also being utilized to determine the abuse liability of flavored cigar products.¹⁰⁴

Cigarette smokers (n=30 completers) will be recruited from advertisements through a variety of media outlets, flyers and the internet. Interested cigarette smokers will contact the University of Minnesota Tobacco Research Programs, be informed about the study and initially screened for eligibility over the telephone or HIPAA compliant website. Subjects who pass initial screening will then be asked to attend a screening visit during which the study will be explained in detail, informed consent will be obtained and the screening questionnaires and procedures will be completed to confirm eligibility. Screening procedures include: Tobacco Use History and Exposure; Fagerstrom Test for Nicotine Dependence (FTND);¹⁰⁵ Wisconsin Index of Smoking Dependence Motives¹⁴⁶; Demographics; Medical History and Current Health Status; Concomitant Medications Questionnaire; Prime MD;¹⁰⁶ Centers for Epidemiological Studies 20-item scale (CES-D);¹⁰⁷ Michigan Alcohol Screening Test (MAST) Short form;¹⁰⁸ Drug Abuse Screening Test (DAST).¹⁰⁹

Eligible participants will be asked to attend a baseline visit in the clinic. Blood pressure and heart rate will be assessed. Confirmation of smoking status will be done using a portable CO device and or a urine sample (NicCheck strip). A urine sample will also be collected to determine pregnancy status for women of childbearing potential. At the end of the baseline visit we will train participants on how to use our Interactive Voice Response System (IVRS). Participants will undergo one week of baseline measurement. Daily surveys will be completed in the IVR to assess frequency of cigarette smoking and other tobacco and marijuana use. This will provide an accurate assessment of whether or not our participants meet the eligibility criteria for smoking and an assessment of potential confounding factors. At the end of this one-week period, participants will be asked to attend 4-half day long laboratory sessions, during which 2 cigarettes (fixed puffing pattern and then *ad libitum*) will be smoked and assessments will be made (Figure 2). Daily IVR surveys will continue until the end of the study.

MEDICAL PROTOCOL (HRP-590)

PROTOCOL TITLE: Sugars Project

VERSION DATE: 22 FEB 2023

The first session for all participants will involve smoking their UB cigarettes. Participants will be asked to refrain from smoking for at least 12 hours prior to each session and must have alveolar CO ≤ 10 ppm to qualify for the session. Subsequently, the IVR records will be examined and vitals (blood pressure and heart rate) will be assessed through an automated cuff to ensure that eligibility criteria are still met. After a 30-minute rest period, participants will complete the MNWS, submit an alveolar CO sample, and will smoke their UB cigarettes in a regimented manner (10 puffs total, 30 seconds between puffs). Five minutes after extinguishing the cigarette, another CO measurement will be taken and participants will be asked to complete the mCEQ, Drug Effects/Liking Questionnaire, MNWS, QSU and Sensory Effects of Smoking Questionnaire, in a specified order via REDCap. The spent cigarette filter will be collected for nicotine analysis. There will be a one- hour interval since the time of cigarette extinction before smoking the next cigarette. During the intervening times between cigarettes, smokers will be allowed to read magazines, listen to neutral podcasts, or watch neutral videos. After this interval, participants will submit another CO, complete the MNWS and smoke their UB cigarettes *ad libitum* within a 10-minute timeframe and the same testing procedures will be followed. Twenty minutes after the second cigarette, the Perceived Health Risk Questionnaire will be administered and then at 30 minutes the Cigarette Purchase Task and Multiple Choice Procedures for the UB cigarettes will be administered. At 50 minutes (2 hours after smoking the first cigarette), participants will be asked to rinse their mouths and oral cells will be collected. At the very end of the session, the Willingness to Switch questionnaire will be administered. Once the Willingness to Switch questionnaire has been completed a number will randomly be selected from the Multiple Choice Procedures task. This will be done by pulling a number 1- 16 out of a jar. The participants will receive either an additional cigarette or the money associated with that number, depending on which choice was made for that number. The participant may choose to smoke the cigarette or not.

In the next three sessions, participants will then be asked to smoke one of three study cigarettes with varying sugar content in a double-blind and counterbalanced order across participant s. Each study cigarette type will be labeled with a symbol (diamond, square or star to minimize ranking bias). Blinding of the cigarettes will occur in [name] laboratory, where staff do not have contact with participants. The same procedures as implemented with UB cigarettes will be followed.

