10.0 Local Number of Participants

10.1 Local Number of Participants to be Consented

Up to 75 smokers will be consented in order to get 30 completers.

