11.0 Local Recruitment Methods

11.1 Recruitment Process

We will recruit up to 75 adult smokers (30 completers) from the Minneapolis-St. Paul metro area who smoke at least 5 cigarettes per day. Smokers will be recruited through the University of Minnesota Tobacco Research Programs. A variety of media will be used that will foster the recruitment across a spectrum of age, education and socioeconomic status, and race/ethnicity.

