15.2 Power Analysis

A total of 30 completed participants will achieve >80% power, for each of the two primary outcomes (satisfaction and crossover point), to detect two sugar conditions (high vs. low)’ difference of a moderate effect size ($d = 0.6$, the target scenario) at a 0.025 (= 0.05/2 primary outcomes) significance level, assuming a moderate correlation between sessions ($r = 0.50$) based on a T^2 test using PASS14 (NLSS, 2015). A total of up to 75 eligible smokers will be enrolled..

We note that because of the uncertainty of the effects of sugars and the range of effect sizes, we chose an effect size that is more conservative but near the range of the effect sizes (based on the endpoint of crossover point from the Multiple Choice Procedure task) used in most studies. The powers of the target scenario and other scenarios by changing the within-subject correlation and effect size, with the fixed sample size ($n = 30$) and type I error ($\alpha = 0.025$), are presented in the table below. We note that the actual power for the factor of sugar level could be larger since 3 sugar levels will be studied.

Scenario	Power	Effect size (d)	Within-subject correlation (r)
Target scenario	0.81	0.6	0.5
	0.89	0.6	0.6
	0.64	0.5	0.5

Other scenarios	0.75	0.5	0.6
	0.92	0.7	0.5
	0.96	0.7	0.6

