15.3 Statistical Analysis

General Approach

All statistical analyses will be performed using SAS or R. All statistical tests will be two-tailed. A Bonferroni adjustment will be used to account for 2 primary endpoints ($p < 0.025$ considered significant). Analyses of the secondary endpoints will not be adjusted ($p < 0.05$ considered significant). Proper transformation such as the logarithm transformation will be used to approximate normality for the outcome variables.

Describing the Study Population

Baseline characteristics of the participants will be summarized using mean and standard deviation (SD) for continuous variables and frequency and percentage for categorical variables.

Primary Analysis

The primary data analysis method will be linear mixed models including the two within-subject factors, sugar condition (2 dummy variables for the medium and high sugar levels) and time (2 dummies for the 3rd and 4th sessions), adjusted for the nicotine levels in spent filters of the first study cigarette used in each of the laboratory sessions (under the fixed puffing pattern). The potential carry-over effect will be tested by including the previous session's condition, i.e., 2 dummies for the previous session being medium and high sugar level (Diggle et al., 2002, p150-153). Note that the usual brand's measure (collected at the 1st session) and other participant-level factors are naturally adjusted across different sugar conditions because of the within-subject design, and hence are not included in the model. However, participant-level factors will be examined for any potential moderating effect (i.e., interaction) as an exploratory analysis.

Subgroup Analysis

Subgroup analyses will be performed for female and male smokers. The analyses will follow the same approach described for the overall group. Note that this study is not powered for detecting the potential interaction of gender and sugar level, however, we will report the size and significance of the interaction together with the subgroup analysis results to provide information for understanding of the role of gender.

Missing data

Every effort will be made to limit the amount of missing data in this trial, and study participants will be incentivized to attend study sessions. We anticipate a high retention rate (>80%) because of the short period of time of this laboratory study.

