We will compare subjects who do and do not complete the study sessions in terms of their baseline characteristics. All observed data will be utilized in the analyses, with missing data being assumed to be missing at random, by using the mixed effects models.

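### The cap of 75 is expected to yield the 30 completers behind the power statement only at the 60% end of the planned 60–65% attrition; the power at the 26–28 completers expected further up that range is not shown

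*Combined protocol and SAP*

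**What the plan says.** Section 5.1 sets the target at 30 completers and then fixes the recruitment ceiling: "Anticipating a 60-65% attrition rate based on current experiences, we will recruit up to 75 participants". Section 10.1 makes the same link: "Up to 75 smokers will be consented in order to get 30 completers". Section 11.1 repeats 75 and 30 together.

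Section 15.2 states: "A total of 30 completed participants will achieve >80% power". This is for the high-versus-low sugar contrast with d = 0.6, within-subject correlation r = 0.50 and a significance level of 0.025 for each of two primary outcomes. Its table varies d and r but holds n at 30. It then adds: "A total of up to 75 eligible smokers will be enrolled".

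Section 15.3 makes all tests two-sided and plans a linear mixed model that uses all observed data. Under missing data it also says: "We anticipate a high retention rate (>80%) because of the short period of time of this laboratory study".

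**The concern.** A ceiling on recruitment and an anticipated attrition rate together fix how many completers to expect. Here the rate is a range, and the ceiling matches only its favourable end. A reader of Section 15.2 sees power for 30 completers and would reasonably take 30 to be what the design is expected to deliver. Over most of the plan's own range fewer are expected, and because the 75 is a ceiling the plan has no stated room to recruit on until 30 is reached. At stake is whether the quoted power describes the trial that is likely to be run, and by how much it would differ.

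A smaller matter is that the 75 are *recruited* in Sections 5.1 and 11.1, *consented* in Section 10.1, and *eligible* and *enrolled* in Section 15.2. Attrition can be checked against plan only if its starting count is clear.

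**Working it through.** **Inputs.** Attrition 60–65% and cap 75 (Section 5.1); 30 completers, d = 0.6, r = 0.5, alpha 0.025 per outcome, T² test (Section 15.2); two-sided tests and the mixed-model terms (Section 15.3).

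**1. Reproduce the plan's power.** For two conditions the T² test is a paired t-test. The standardised difference is dz = d/√(2(1 − r)) = 0.6/√(2 × 0.5) = 0.6. The noncentrality is dz × √n = 0.6 × √30 = 3.286, with n − 1 = 29 degrees of freedom and a two-sided critical value of 2.364. Power is 0.816; the plan prints 0.81. The other five rows of the table give 0.898, 0.647, 0.754, 0.923 and 0.968 against printed 0.89, 0.64, 0.75, 0.92 and 0.96. All six agree within 0.01, and the printed values look truncated rather than rounded.

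**2. Expected completers from the cap.**
- 60% attrition: 75 × 0.40 = 30.0
- 62.5% attrition: 75 × 0.375 = 28.1
- 65% attrition: 75 × 0.35 = 26.25

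Working backwards, 30/(1 − 0.60) = 75 exactly, so the cap contains no margin above 60%.

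**3. Power at those numbers, target scenario.** The paired calculation uses n − 1 degrees of freedom. The mixed-model figure keeps the same noncentrality and uses pooled within-subject degrees of freedom. With 3n observations, n subjects, two condition dummies and two session dummies, these are 3n − n − 4 = 2n − 4. One fewer for the nicotine covariate changes the result by no more than 0.001.

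| Completers | Attrition giving this number in expectation | Paired (T²) power | Mixed model, completers only |
|---|---|---|---|
| 30 | 60% | 0.816 | 0.834 |
| 28 | about 62.5% | 0.784 | 0.804 |
| 26 | about 65% | 0.746 | 0.770 |

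By the paired calculation power is still 0.800 at 29 completers, which are expected up to 1 − 29/75 = 61.3% attrition. By the mixed model it is 0.804 at 28, expected up to 1 − 28/75 = 62.7%.

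**4. Partial completers.** The mixed model also uses sessions from people who leave early. The plan does not say how many such people to expect, so this step is an assumption. Suppose the retention figure in Section 15.3 counts from the first laboratory session, and take 80%. At 65% attrition, 26.25/0.80 = 32.8 people start sessions and 32.8 − 26.25 = 6.6 leave part-way. Generalised least squares with a random intercept (r = 0.5), balanced orders, and condition and session terms gives:
- no partial data: 0.774 (at 26.25 completers);
- the 6.6 spread evenly over three exit points, so that 2.2 contribute two study sessions and 2.2 contribute one: 0.80;
- 3.3 contributing two sessions and 3.3 contributing one: 0.81.

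The nicotine covariate is ignored here. Retention above 80% would mean fewer partial completers and a smaller gain.

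**The case against.** **The power statement is conditional and true.** Section 15.2 ties its claim to 30 completers in the same sentence, and the figure reproduces. This stands in full. A reader might infer that the power calculation is wrong or that its condition is hidden; neither is so. What remains is that the plan gives no power for the completer numbers its own attrition range implies.

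**The planned analysis is not a completers-only t-test.** This also stands. It raises the figure at 26 completers from 0.75 to about 0.77, and perhaps to about 0.80 with partial data. The last step depends on a dropout pattern that the plan does not give, so it cannot be relied on, but it does keep the size of the problem small.

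**The range is only a forecast, and the table already shows wider uncertainty.** Power in the table runs from 0.64 to 0.96 as d and r vary, so a drop of 0.07 is small beside it. That is a fair argument on severity. It does not explain why n alone is held at its most favourable value.

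**The terms for the 75 can be reconciled.** A reader might see a contradiction, because Section 5.1 has a visit at which "informed consent will be obtained and the screening questionnaires and procedures will be completed to confirm eligibility". But Sections 5.1 and 8.3 also describe eligibility pre-screening before that visit, so the eligible smokers of Section 15.2 can be the same 75 who are consented under Section 10.1. This is mostly a matter of wording.

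**The two loss rates can be reconciled.** Anticipated attrition of 60–65% beside retention above 80% invites the inference that the plan contradicts itself. The documents do not support that. Section 15.3 goes on: "We will compare subjects who do and do not complete the study sessions in terms of their baseline characteristics". In that setting the retention figure most naturally concerns people already in the laboratory sessions, whereas the attrition figure can include losses before the sessions begin.

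**Conclusion.** The point holds as a minor one. On the plan's figures the cap of 75 meets the 30-completer target in expectation only at 60% attrition; about 28 completers are expected at 62.5% and about 26 at 65%. In the target scenario, power across the stated range is then about 0.82 down to 0.75 by the plan's own method, or about 0.83 down to 0.77 under the mixed model on completers only. The largest loss is four completers and about 0.07 in power.

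The paired figures rest only on the plan's d, r and alpha, and on applying the attrition rate to the full 75. The mixed-model figures add the assumption of pooled degrees of freedom, with no gain or loss of precision from the nicotine covariate. Whether partial completers bring the 65% end back to about 0.80 depends on a dropout pattern that the plan does not state.

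A reader might conclude that the cap must be raised. That does not follow: the shortfall is modest, and stating it is enough.

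**What to change.** Keep 30 completers as the target and add to Section 15.2:

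> With up to 75 participants and 60–65% attrition, about 26–30 completers are expected; power in the target scenario is then about 0.75–0.81 by the paired (T²) calculation on completers, and about 0.77–0.83 under the mixed model before any contribution from partial completers.

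The upper figure of 0.81 follows the value printed in the plan's table; rounded, it would be 0.82.

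Use one term for the 75 in Sections 5.1, 10.1, 11.1 and 15.2. *Consented*, as in Section 10.1, is the natural choice, but the sponsor should confirm that this is the count meant.

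The cost is wording only. The one drawback is that the lower end of the stated power becomes slightly less favourable.
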